## 7.1. Time and Events Table

Procedure	Screening (up to 30 days prior to scan)	Scanning visit	Follow-up (2-4 weeks post-last dose)	Notes
Informed consent	X			
Inclusion and exclusion criteria	X			
Demography	X			
Brief physical	X	X	X	On the scanning day, to be completed pre-scan, prior to the administration of the peptide.
Medical / Medical history	X			
Vital signs	X	X		On the scanning day, to be conducted pre and post scan.
12-lead ECG	X			
Alcohol breath test	X	X		
Urine drug and cotinine screen	X			
Healthy subjects only: spirometry	X			
Coagulation profile	X			This will include PT (Prothrombin time), APTT (Activated Partial Thromboplastin Time) and Thrombin Time (TT)
PAH patients only (who have been on Warfarin): INR		X		Sample to confirm suitability for scanning day can be done up to 3 days prior to the day of the scan
HIV, Hep B and Hep C screen	X			If test otherwise performed within 3 months prior to first dose of study treatment, testing at screening is not required
Clinical chemistry and Haematology	X			
Urinalysis	X			
Allen's test	X	X		
i.v dose of [  C]-GSK2256098		X		
PET scan		X		PET scanning will be started at the same time as injection of the radioligand and PET data will be collected for up to 90 minutes post administration.

Procedure	Screening (up to 30 days prior to scan)	Scanning visit	Follow-up (2-4 weeks post-last dose)	Notes
Attenuation CT scan		X		Lasting seconds to minute prior to start of PET scan. If subject gets off the bed for a comfort break midway through the PET scan, another CT scan will be performed prior to re-starting acquisition of PET data
Genetics sample		X		Genetic Informed consent must be obtained before collecting a sample
Samples for plasma radioactivity measurements & whole blood		X		Blood samples will be collected during scanning for plasma and whole blood radioactivity measurements.
AE/SAE review		X	X	
Concomitant medication review	X	X	X	

## 7.2. Screening and Critical Baseline Assessments

Cardiovascular medical history/risk factors (as detailed in the CRF) will be assessed at screening.

The following demographic parameters will be captured: year of birth, sex, race and ethnicity.

Medical/medication/family history will be assessed as related to the inclusion/exclusion criteria listed in Section 5.

Procedures conducted as part of the subject's routine clinical management (e.g. MRI, INR) and obtained prior to signing of informed consent may be utilized for Screening or baseline purposes provided the procedure meets the protocol-defined criteria and has been performed in the timeframe of the study.

## 7.3. Safety

Planned time points for all safety assessments are listed in the Time and Events Table (Section 7.1). Additional time points for safety tests (such as vital signs, physical exams and laboratory safety tests) may be added during the course of the study based on newly available data to ensure appropriate safety monitoring.

### 7.3.1. Adverse Events (AE) and Serious Adverse Events (SAEs)

The definitions of an AE or SAE can be found in [Appendix 3](#).

The investigator and their designees are responsible for detecting, documenting and reporting events that meet the definition of an AE or SAE.

#### 7.3.1.1. Time period and Frequency for collecting AE and SAE information

- Any SAEs assessed as related to study participation (e.g., protocol-mandated procedures, invasive tests, or change in existing therapy) or related to a GSK product will be recorded from the time a subject consents to participate in the study up to and including any follow-up contact.
- AEs will be collected from the start of the PET scan until the follow-up contact (see Section 7.3.1.3), at the timepoints specified in the Time and Events Table (Section 7.1).
- Medical occurrences that begin prior to the start of study treatment but after obtaining informed consent may be recorded on the Medical History/Current Medical Conditions section of the CRF.
- All SAEs will be recorded and reported to GSK within 24 hours, as indicated in [Appendix 3](#).
- Investigators are not obligated to actively seek AEs or SAEs in former study subjects. However, if the investigator learns of any SAE, including a death, at any time after a subject has been discharged from the study, and he/she considers the

event reasonably related to the study treatment or study participation, the investigator must promptly notify GSK.

NOTE: The method of recording, evaluating and assessing causality of AEs and SAEs plus procedures for completing and transmitting SAE reports to GSK are provided in [Appendix 3](#).

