		
subjects blood coagulation profile. Arterial cannulation will be performed by suitably trained staff under local anaesthetic, using best practice. On completion of the PET scan, the radial artery cannula will be removed and subjects observed until haemostasis obtained. The PAH patients will be at an increased risk of bruising and will not be discharged until the Investigator is happy with the cannulation site. The total amount of blood collected for all of the study procedures will not exceed 500 mL.
 
Warfarin will be discontinued in subjects on prophylactic doses about 5 days before the arterial cannulation. Arterial cannulation will be performed with an INR ideally <math>\leq 2</math>. In situations where, anticoagulation is administered with a therapeutic intent (rather than simply prophylaxis), warfarin will be substituted by Low Molecular weight heparin starting up to 5 days prior to until a time after completion of the PET scan when therapeutic anti-coagulation is considered to have been achieved in the views of the clinician.

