### 5.3. Screening Failures

Screen failures are defined as subjects who consent to participate in the clinical trial but are never subsequently scanned. In order to ensure transparent reporting of screen failure subjects, meet the Consolidated Standards of Reporting Trials (CONSORT) publishing requirements, and respond to queries from Regulatory authorities, a minimal set of screen failure information is required including Demography, Screen Failure details, Eligibility Criteria, and Serious Adverse Events (see Section 7.3.1.5).

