### 7.3.7. Positron Emission Tomography (PET)

Prior to the commencement of the PET scan a venous cannula will be inserted in to the subjects arm for administration of [C]-GSK2256098. A radial arterial cannula will also be inserted prior to the scan start under local anaesthesia from which blood samples will be collected throughout the scan to enable the quantification of the total unmetabolised [C]-GSK2256098 related radioactivity in the whole blood and plasma throughout the duration of the PET scan. Initially an X-ray topogram of the area will be performed to localise the area to be scanned followed by a low- dose CT attenuation scan of the area to

be scanned. Thereafter the PET scan will commence with the administration of [C]-GSK2256098 intravenously and the emission data will be acquired for up to 90 minutes post-administration. The data provided from the arterial blood samples collected will be used to derive an input function for the analysis of emission PET data. At the end of the scan, the cannulae will be removed.

Ideally, subjects will complete the PET scan without a break. However, subjects may be removed from the scanner once for a period of rest and repositioned to continue the PET scan if absolutely necessary. The primary discomfort arises from the need for subjects to lie supine during the scan. The scan will be stopped or abandoned if the subject is unable to complete the scan.

The subjects will be monitored for approximately one hour after completion of the scan and will be allowed home at the Investigator's discretion.

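### Non-serious AE collection opens at tracer injection, so non-serious procedure-related events confined to the period before injection, or in subjects cannulated but never injected, have no required AE record

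*Protocol*

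**What the plan says.** Protocol 7.3.1.1 sets three tiers.

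- **SAEs** related to study participation or to a GSK product are recorded from consent. The examples of study participation are "protocol-mandated procedures, invasive tests, or change in existing therapy".
- **Non-serious AEs** start later: "AEs will be collected from the start of the PET scan until the follow-up contact".
- **Other medical occurrences** between consent and study treatment "may be recorded on the Medical History/Current Medical Conditions section of the CRF".

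The Time and Events Table (7.1) fixes the start of the scan: "PET scanning will be started at the same time as injection of the radioligand". Section 7.3.7 puts both cannulae before that point: "Prior to the commencement of the PET scan a venous cannula will be inserted in to the subjects arm", and "A radial arterial cannula will also be inserted prior to the scan start under local anaesthesia". The risk table in 4.5.1 puts the anticoagulation change earlier still: "Warfarin will be discontinued in subjects on prophylactic doses about 5 days before the arterial cannulation". Where anticoagulation is therapeutic, heparin substitution begins up to 5 days ahead and runs on past the scan.

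Section 5.3 classes anyone who consents but is never scanned as a screen failure, for whom "a minimal set of screen failure information is required including Demography, Screen Failure details, Eligibility Criteria, and Serious Adverse Events".

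**The concern.** The tracer is given as a microdose with no clinically significant pharmacology expected (Protocol 4.5). The risk table in 4.5.1 names two study-procedure risks, radiation and arterial cannulation, and cannulation is the only invasive one. The table also notes a raised bruising risk in PAH patients. Yet the non-serious AE window opens only after the cannulae are in and after any warfarin change has begun.

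Section 7.3.1.1 already treats invasive tests and changes in existing therapy as sources of harm from consent onward, but only when the harm is serious. What is at stake is the tolerability record for the study procedures. It matters most when a failed or poorly tolerated cannulation is the reason that a subject was never scanned.

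**Working it through.** The plan states no figure on this point, so the check sets the order of events against the collection rule.

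| Step | Timing | Source | Non-serious AE record required? |
|---|---|---|---|
| Consent and screening | up to 30 days before the scan | Protocol 7.1 | No |
| Warfarin stopped, or heparin substituted | about 5, or up to 5, days before | Protocol 4.5.1 | No |
| Venous and radial cannulae | before scan start | Protocol 7.3.7 | No |
| Topogram and attenuation CT | before scan start | Protocol 7.3.7 | No |
| Injection, which is the PET start | scan day | Protocol 7.1, 7.3.7 | Window opens |
| Scan, cannula removal, about one hour of monitoring | scan day | Protocol 7.3.7 | Yes |
| Follow-up | 2 to 4 weeks after the last dose | Protocol 7.1 | Window closes |

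1. **Before the window.** Four steps precede it. Related SAEs are required throughout them. For anything else, the stated route is the optional medical-history entry.

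2. **What the window recovers.** Protocol 12.3.1 counts as AEs conditions first detected after study treatment, even if present earlier, and exacerbations of existing ones. What remains outside is an event that starts, is noticed and does not worsen before injection, or any non-serious event in a subject never injected.

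3. **Indirect routes.** The pre-scan physical, vital signs, concomitant-medication review, open questioning (7.3.1.2) and screen-failure details may each leave a trace. The physical is fixed only as before tracer administration, so it may precede cannulation. None of these routes requires the intensity and causality assessments that 12.3.5 demands for an AE. The SAP's list of listings (16.2) has no medical-history listing; only the general sentence in Protocol 9.4.2 would bring such entries into reporting.

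4. **AE definition.** Protocol 12.3.1 ties an AE to use of a medicinal product, and 12.3.2 says that an event that is not an AE cannot be an SAE. A venous-cannula injury before any product is given may fail that definition, yet 7.3.1.1 collects related procedural SAEs from consent. The three sections need reconciling.

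5. **SAP.** The Safety Population (SAP 9) contains dosed subjects only, and SAP 13.1 says that all analyses use it. SAP 14.1 lists all adverse events without naming a population. An undosed subject's event could therefore be left out even if collected.

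6. **Scale.** Subjects passing through the interval from cannulation to injection: 5 + 5 = 10 at the initial target and 12 + 12 = 24 at the planned maximum, before any replacements. These are sample sizes, not counts of harm. The current window runs from injection to follow-up, 14 to 28 days. Starting at consent would add 0 to 30 days for an injected subject, for study-related events only. The documents give no event rate, no time from cannulation to injection and no count of warfarin users, so the number of unrecorded events cannot be estimated.

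**The case against.** The tiered rule is deliberate, and much of it works. The arterial cannula stays in during the scan. Subjects are then observed until bleeding has stopped, PAH patients leave only when the investigator is content with the site, and everyone is monitored for about an hour. Bruising, the cannulation harm that the risk table names, will often appear or worsen in that period and so be an AE. Heparin substitution also extends past the scan. The screen-failure data set is a minimum, and a failed cannulation would naturally be entered in its details. Sections 7 and 7.3 allow assessments to be added. All of this stands, and it makes the gap narrow. It does not turn an optional entry into a required AE record.

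Three stronger readings are tempting, and the documents support none of them.

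- A reader might infer that cannulation harm in general goes unrecorded. It does not: events appearing or worsening after injection, and related SAEs from consent, are captured.
- A reader might see a contradiction between the SAE and AE start points. They are different rules for different tiers, which is a design choice.
- A reader might suppose that moving the start date is enough. It is not, because of the AE definition in 12.3.1, the missing end point for undosed subjects and the SAP's population rule.

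**Conclusion.** The point holds in its limited form. The rule leaves a small class of non-serious procedural events without a required AE record, and the indirect routes do not replace one. The effect is confined to completeness of the tolerability record; no primary result or stopping decision depends on it. It is a cheap improvement, not a flaw that threatens the study.

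This rests on three readings: that scan start means injection, as 7.1 and 7.3.7 both say; that the medical-history entry is optional as worded; and that the screen-failure set, although a minimum, does not itself require non-serious AEs.

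**What to change.** - **Protocol 7.3.1.1:** collect non-serious AEs assessed as related to study participation from consent, with the scope already used for related SAEs.
- **Protocol 12.3.1, 12.3.2 and 12.3.5:** state that events related to study procedures count as AEs even before any product is given, so that the definitions agree with the from-consent SAE rule. Record causality for these events as relation to study participation; 12.3.5 now asks only about study treatment.
- **Protocol 5.3:** add these events to the screen-failure data set. Define when collection ends for subjects never injected, for example at the last study contact, because follow-up in 7.1 is timed from the last dose.
- **SAP 14.1:** list these events for all consented subjects, flagged as not treatment-emergent with the field already in the AE listing shell. State this as an exception to the Safety Population rule in SAP 9 and 13.1. The treatment-emergent tables stay as they are.

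The cost is a wording and CRF change and a few more AE records. Subjects who reach the scanning visit need no extra visit, since AE review is already scheduled then and the questions in 7.3.1.2 reach back to the last contact. Those who drop out before it may need one contact. No clinical rule changes.

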#### **7.3.1.2. Method of Detecting AEs and SAEs**

Care will be taken not to introduce bias when detecting AEs and/or SAEs. Open-ended and non-leading verbal questioning of the subject is the preferred method to inquire about AE occurrence. Appropriate questions include:

- “How are you feeling?”
- “Have you had any (other) medical problems since your last visit/contact?”
- “Have you taken any new medicines, other than those provided in this study, since your last visit/contact?”

#### **7.3.1.3. Follow-up of AEs and SAEs**

After the initial AE/SAE report, the investigator is required to proactively follow each subject at subsequent visits/contacts. All SAEs, and non-serious AEs of special interest (as defined in Section [4.5.1](#)) will be followed until resolution, until the condition stabilizes, until the event is otherwise explained, or until the subject is lost to follow-up (as defined in Section [5.4](#)). Further information on follow-up procedures is given in [Appendix 3](#).

#### **7.3.1.4. Cardiovascular and Death Events**

For any cardiovascular events detailed in [Appendix 3](#) and all deaths, whether or not they are considered SAEs, specific Cardiovascular (CV) and Death sections of the CRF will be required to be completed. These sections include questions regarding cardiovascular (including sudden cardiac death) and non-cardiovascular death.

The CV CRFs are presented as queries in response to reporting of certain CV MedDRA terms. The CV information should be recorded in the specific cardiovascular section of the CRF within one week of receipt of a CV Event data query prompting its completion.

The Death CRF is provided immediately after the occurrence or outcome of death is reported. Initial and follow-up reports regarding death must be completed within one week of when the death is reported.

#### **7.3.1.5. Regulatory Reporting Requirements for SAEs**

Prompt notification by the investigator to GSK of SAEs related to study treatment (even for non- interventional post-marketing studies) is essential so that legal obligations and ethical responsibilities towards the safety of subjects and the safety of a product under clinical investigation are met.

GSK has a legal responsibility to notify both the local regulatory authority and other regulatory agencies about the safety of a product under clinical investigation. GSK will comply with country specific regulatory requirements relating to safety reporting to the regulatory authority, Institutional Review Board (IRB)/Independent Ethics Committee (IEC) and investigators.

Investigator safety reports are prepared for suspected unexpected serious adverse reactions according to local regulatory requirements and GSK policy and are forwarded to investigators as necessary.

An investigator who receives an investigator safety report describing a SAE(s) or other specific safety information (e.g., summary or listing of SAEs) from GSK will file it with the IB and will notify the IRB/IEC, if appropriate according to local requirements.

#### **7.3.2. Pregnancy**

- Details of all pregnancies in female partners of male subjects will be collected after the PET scan and until the follow-up visit.
- If a pregnancy is reported then the investigator should inform GSK within 2 weeks of learning of the pregnancy and should follow the procedures outlined in [Appendix 4](#).

#### **7.3.3. Physical Exams**

- A brief physical examination will include, at a minimum assessments of the skin, lungs, cardiovascular system, and abdomen (liver and spleen).
- Investigators should pay special attention to clinical signs related to previous serious illnesses

#### **7.3.4. Vital Signs**

- Vital signs will be measured in semi-supine position after 5 minutes rest and will include temperature, systolic and diastolic blood pressure, pulse rate and respiratory rate.

#### **7.3.5. Electrocardiogram (ECG)**

- Single 12-lead ECGs will be obtained at each timepoint during the study using an ECG machine that automatically calculates the heart rate and measures PR, QRS, QT, and QTcF intervals.

#### **7.3.6. Clinical Safety Laboratory Assessments**

All protocol required laboratory assessments, as defined in [Table 1](#), must be conducted in accordance with the Laboratory Manual, and Protocol Time and Events Schedule.

Laboratory requisition forms must be completed and samples must be clearly labelled with the subject number, protocol number, site/centre number, and visit date. Details for the preparation and shipment of samples will be provided by the laboratory and are detailed in the site SOPs. Reference ranges for all safety parameters will be provided to the site by the laboratory responsible for the assessments.

If additional non-protocol specified laboratory assessments are performed at the institution's local laboratory and result in a change in subject management or are considered clinically significant by the investigator (e.g., SAE or AE or dose modification) the results must be recorded in the CRF.

Refer to the site SOPs for appropriate processing and handling of samples to avoid duplicate and/or additional blood draws.

Haematology, clinical chemistry, urinalysis and additional parameters to be tested are listed in [Table 1](#).

**Table 1 Protocol Required Safety Laboratory Assessments**

Laboratory Assessments	Parameters			
Haematology	Platelet Count	RBC Indices:	WBC count with Differential:	
	RBC Count	MCV	Neutrophils	
	Hemoglobin	MCH	Lymphocytes	
	Hematocrit	MCHC	Monocytes	
			Eosinophils	
			Basophils	
Clinical Chemistry	BUN	Potassium	AST (SGOT)	Total and direct bilirubin
	Creatinine	Sodium	ALT (SGPT)	Total Protein
	Glucose	Calcium		Albumin
Routine Urinalysis	
 
Specific gravity
 
pH, glucose, protein, blood and ketones by dipstick
 
Microscopic examination (if blood or protein is abnormal)
 
			
Other Screening Tests	
 
HIV
 
Hepatitis B (HBsAg)
 
Hepatitis C (Hep C antibody)
 
FSH and estradiol (as needed in women of non-child bearing potential only)
 
Pregnancy test
 
Alcohol and drug screen (to include at minimum: amphetamines, barbiturates, cocaine, opiates, benzodiazepines and cannabinoids)
 
			

### 7.3.7. Positron Emission Tomography (PET)

Prior to the commencement of the PET scan a venous cannula will be inserted in to the subjects arm for administration of [C]-GSK2256098. A radial arterial cannula will also be inserted prior to the scan start under local anaesthesia from which blood samples will be collected throughout the scan to enable the quantification of the total unmetabolised [C]-GSK2256098 related radioactivity in the whole blood and plasma throughout the duration of the PET scan. Initially an X-ray topogram of the area will be performed to localise the area to be scanned followed by a low- dose CT attenuation scan of the area to

be scanned. Thereafter the PET scan will commence with the administration of [C]-GSK2256098 intravenously and the emission data will be acquired for up to 90 minutes post-administration. The data provided from the arterial blood samples collected will be used to derive an input function for the analysis of emission PET data. At the end of the scan, the cannulae will be removed.

Ideally, subjects will complete the PET scan without a break. However, subjects may be removed from the scanner once for a period of rest and repositioned to continue the PET scan if absolutely necessary. The primary discomfort arises from the need for subjects to lie supine during the scan. The scan will be stopped or abandoned if the subject is unable to complete the scan.

The subjects will be monitored for approximately one hour after completion of the scan and will be allowed home at the Investigator's discretion.

